3.1 Overall Logic Model

3.1.1 Graphical explanation of core elements

The logic model systematically depicts each component of the research and their interconnections. At the “input” level, the study invests essential resources—community training venues, smart RT equipment, and professional supervisors—while accounting for participant characteristics such as age, sex, baseline health status, and eHealth literacy. The “activities” component refers to the smart RT intervention delivered by trained community workers following prescribed frequency, intensity, and duration protocols. Direct “outputs” include training adherence (attendance rate, training completion rate) and actual training “dose” (cumulative training volume), reflecting intervention execution fidelity. These outputs generate “short-term outcomes”: improved BMD, enhanced physical function (muscle strength, balance), and increased QoL scores after 8 months. Mechanistic indicators, notably grip-strength change (Δ HGS), are also monitored to explore the mediating role of muscle strength. In the long term, the intervention is expected to reduce fracture risk and demonstrate “cost-effectiveness” at the health-economic level. Several moderating factors—community environment support, technology acceptance, socioeconomic status, and the digital divide—may influence adherence and effect magnitude.

In Figure 3.1, arrows represent causal pathways: from input resources and participant

characteristics, through the RT intervention, influencing adherence and dose, producing short-term improvements in physical and quality-of-life outcomes, and ultimately accumulating into long-term fracture-risk reduction and cost-effectiveness.

3.1.2 Six sub-studies within the model

The logic model pre-specifies six core pathways corresponding to six sub-studies, each grounded in a specific hypothesis (H1–H6). H1 focuses on predictive factors for intervention response, hypothesising that baseline characteristics and eHLQ scores significantly influence RT responsiveness. H2 addresses dose–response relationships, proposing a nonlinear (J- or U-shaped) association between training dose and outcomes. H3 examines the mediating mechanism, positing that grip-strength improvement (Δ HGS) partially mediates the intervention’s effect on BMD. H4 investigates the moderating role of technology acceptance on adherence and outcomes. H5 explores QoL trajectory heterogeneity, anticipating at least two distinct trajectory classes with differential clinical associations. H6 addresses economic evaluation, hypothesising that the ICER falls within an acceptable WTP threshold.

3.2 Primary Research Hypotheses (H1–H6)

3.2.1 H1 (Sub-study 1)

Among older adults with primary OP receiving the smart RT intervention, baseline health status and health literacy differentially influence RT response. Specifically, participants with lower baseline BMD but higher eHLQ/technology acceptance scores are more likely to achieve clinically significant BMD improvement ($\geq 3\%$ lumbar spine increase). The rationale is twofold: lower baseline BMD provides greater room for improvement, and higher health literacy and technology acceptance enable more complete understanding and execution of the training protocol.

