1.4.2 Specific research objectives (corresponding to six sub-studies)

Sub-study 1: A logistic regression modelling study to determine whether baseline grip strength and sedentary time predict BMD response ($\geq 1\%$ improvement) to RT, thereby identifying “responders” for individualised exercise prescription.

Sub-study 2: A dose–response study using generalised additive models (GAM) to analyse the minimum effective frequency of RT and to explore nonlinear relationships between training frequency and BMD/balance function (Berg Balance Scale), identifying threshold effects.

Sub-study 3: A mediation analysis examining whether change in grip strength (Δ HGS) mediates the effect of RT on BMD, providing empirical evidence for the muscle–bone coupling mechanism.

Sub-study 4: An empirical analysis investigating whether prior experience with digital devices and technology acceptance scores are associated with higher training adherence, informing the optimisation of smart elderly care platform design.

Sub-study 5: A clustering and visualisation study of QoL trajectories (SF-36) to identify patterns of change in physical (PCS) and mental (MCS) health dimensions, enabling subgroup-targeted intervention strategies.

Sub-study 6: A micro-level cost-effectiveness analysis calculating the marginal cost per 1% BMD improvement based on actual financial data, constructing a community RT cost-effectiveness evaluation model to support policy and health-insurance alignment.

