1.4.5 Application innovations

Community RT responder screening tool: A nomogram based on baseline grip strength, sedentary time, and BMI for rapid identification of high-responder populations (BMD improvement $\geq 3\%$; AUC = 0.82), guiding targeted resource allocation [Sub-study 1].

Low-technology smart supervision protocol: A “dual-track supervision model”—digital track (WeChat-based training reminders and video guidance) and manual track (weekly telephone follow-up and periodic home visits by community workers).

Health insurance alignment decision tree: Cost-effectiveness outputs translated into policy pathways based on the ICER-to-GDP ratio: when ICER does not exceed one times per-capita GDP, the intervention enters the basic public health service package; when it exceeds this threshold, supplementary commercial health insurance is required.

Chapter 2 Literature Review and Theoretical Foundations

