2.2.3 Sources of heterogeneity in the evidence

Variability across studies arises from three principal sources. First, intervention protocol differences: training frequency of three sessions per week significantly improves BMD at multiple sites, interventions lasting ≥ 48 weeks significantly affect femoral neck and total hip BMD, and 40-minute sessions significantly improve lumbar spine BMD [42]. Second, participant characteristics: a 2021 study of 275 older adults aged 62–70 showed that following 9 weeks of progressive RT (three sessions per week), male participants gained 63 mm² in vastus lateralis cross-sectional area versus 20 mm² in females [45]. Third, measurement method differences: variations across DXA device models introduce BMD measurement error [46],

and different functional assessment tools yield varying sensitivity and specificity for fall prediction [47]. Standardisation of study design is therefore essential to reduce variability.

2.2.4 Gaps in the evidence for long-term community application, smart implementation, and individualisation

Three major evidence gaps persist. First, community long-term application evidence is insufficient: the majority of studies were conducted in controlled laboratory or clinical settings, with only three identified trials taking place in real-world community environments; community adherence rates and post-cessation effect maintenance remain unknown. Second, smart implementation research is absent: no study has systematically integrated intelligent devices and platforms (e.g., app-guided training, wearable sensors) into RT; most wearable devices serve monitoring functions only, and the impact of older adults' technology acceptance on outcomes has not been quantified. Third, individualised strategies are lacking: despite known responder variability, predictive tools to identify who will benefit most from RT are unavailable. These gaps collectively motivate the present study to validate long-term effectiveness in real community settings, explore smart-technology enhancement pathways, and develop individualised intervention tools.

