4.1.2 Nested sub-study designs

Six sub-studies are nested within the primary RCT framework. Sub-study 1: predictive model development (TRIPOD guidelines). Sub-study 2: observational dose–response analysis (STROBE statement). Sub-study 3: causal mediation analysis using a counterfactual framework. Sub-study 4: interaction-effect analysis via mixed-effects modelling with interaction terms. Sub-study 5: longitudinal trajectory modelling using group-based trajectory modelling (GBTM) or latent class growth modelling (LCGM). Sub-study 6: trial-based economic evaluation with ICER calculation (CHEERS checklist).

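### H1 studies only trained participants and calls a within-person BMD rise a response to training, so Sub-study 1 can forecast who will gain under the programme but not who gains because of training.

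*Protocol*

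**What the plan says.** Section 3.2.1 (H1) sets the population: "Among older adults with primary OP receiving the smart RT intervention, baseline health status and health literacy differentially influence RT response". It predicts that "participants with lower baseline BMD but higher eHLQ/technology acceptance scores are more likely to achieve clinically significant BMD improvement", defined as a lumbar spine rise of at least 3%, partly because "lower baseline BMD provides greater room for improvement".

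Section 1.4.2 describes Sub-study 1 as "A logistic regression modelling study to determine whether baseline grip strength and sedentary time predict BMD response", with the cut at 1% and the response attributed to resistance training. The purpose given is to identify responders so that exercise can be prescribed individually.

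Section 1.4.5 turns this into a nomogram built on grip strength, sedentary time and BMI, "for rapid identification of high-responder populations" (cut at 3%), to guide where resources go. Section 2.2.4 states the need that the study is meant to meet: "predictive tools to identify who will benefit most from RT are unavailable".

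Section 4.1.2 gives the method as "Sub-study 1: predictive model development (TRIPOD guidelines"). It names interaction terms only for Sub-study 4, which concerns technology acceptance.

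Section 4.1.1 describes a 1:1 randomised trial. The schedule in section 3.3.4 places DXA at T0 and T2 without restriction by arm. Section 3.3.3 lists osteoporosis medication, comorbidity, calcium and vitamin D adequacy, and baseline activity as covariates to be controlled.

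**The concern.** Benefit from training is the difference between a person's BMD with training and without it. A model fitted only in trainees estimates the chance of a given change from baseline. That change mixes the training effect with natural course, any co-treatment effect left after adjustment, and scan error. A baseline factor that goes with BMD change in anyone, trained or not, then looks like a predictor of response to training. The nomogram could direct community resources to people whose BMD would have risen anyway.

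A second, narrower problem concerns one predictor. H1 expects people with lower baseline BMD to respond more often, but response is a percentage of that same baseline. The lower the baseline, the smaller the absolute gain needed to reach 3%, so this part of H1 can appear confirmed with no difference in absolute gain.

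**Working it through.** **The plan's own figure.** The only number given for the Sub-study 1 tool is an AUC of 0.82 (section 1.4.5). No data or derivation accompany it, so it cannot be reproduced. The checks below ask how far the responder label can depart from benefit.

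**Inputs.** From the protocol: scan CV about 1% (section 4.4.1); cuts of 3% (sections 1.4.5 and 3.2.1) and 1% (section 1.4.2). The protocol gives no SD of BMD change and no baseline distribution. Assumed, therefore: true between-person SD of change *b* = 0 to 3 percentage points; mean untrained change *m* = 0 or -0.5%; a training effect of +3 points for everyone.

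**1. Scan error alone.** SD of a change = √2 × 1% = 1.41%. With no true change:
- P(change ≥ 1%) = P(Z ≥ 1/1.41) = 24.0%
- P(change ≥ 3%) = P(Z ≥ 3/1.41) = 1.7%

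**2. Share of 3% responders who needed no training.** SD of observed change = √(2 × 1² + b²). Because the assumed effect is the same for everyone, all who would reach 3% untrained also reach it trained. The share is therefore P(≥3 | mean m) / P(≥3 | mean m + 3).

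| b | SD of change | m = 0: untrained / trained → share | m = -0.5: untrained / trained → share |
|---|---|---|---|
| 0 | 1.41 | 1.7% / 50% → 3% | 0.7% / 36.2% → 2% |
| 1 | 1.73 | 4.2% / 50% → 8% | 2.2% / 38.6% → 6% |
| 2 | 2.45 | 11.0% / 50% → 22% | 7.7% / 41.9% → 18% |
| 3 | 3.32 | 18.3% / 50% → 37% | 14.6% / 44.0% → 33% |

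The range is about 2 to 37%, and it turns mainly on *b*, which the protocol does not give.

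**3. Can a training-arm AUC show benefit?** This was simulated with 300,000 people per scenario: a marker that shifts BMD change equally in both arms by 1 or 2 points per SD, mean untrained change -0.5%, other true variation of SD 1.5 points, and 1% scan error.
- With no training effect, the AUC for 3% response in the training arm was 0.75 to 0.87, and about the same in controls.
- With a uniform 3-point effect, the training-arm AUC was 0.70 to 0.83, while the between-arm benefit was 3.0 points in both the high and the low marker third.

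A good AUC in trainees is therefore compatible with no difference in benefit. An arm-by-marker term would correctly be null.

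**4. Baseline BMD as denominator (H1's baseline-BMD prediction only).** A 3% rise needs 0.03 × 0.65 = 0.0195 g/cm2 at baseline 0.65, and 0.03 × 0.85 = 0.0255 g/cm2 at baseline 0.85. Assume one distribution of absolute gain for everyone, with mean 0.020 g/cm2:
- SD 0.020: 51.0% versus 39.2% respond, odds ratio 1.62
- SD 0.030: 50.7% versus 42.7% respond, odds ratio 1.38

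The odds ratio is about 1.4 to 1.6 with no difference in absolute gain.

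**The case against.** **Predicting who reaches a gain under the programme is a legitimate question, and section 4.1.2 declares a prediction model.** This stands. A training-arm model answers that question. It does not answer the one posed in sections 1.4.2, 1.4.5 and 2.2.4, which speak of response to training and of who benefits.

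**Section 3.3.3 controls for medication and nutrition.** This stands in part. A reader might infer that drug treatment or diet will be labelled as predictors of training response. The protocol does not support that, because both are listed for adjustment. But covariate adjustment within one arm cannot supply the untrained outcome. Natural course remains, as do co-treatment effects not captured; section 3.3.4 schedules medication use at baseline only.

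**The denominator problem does not reach the screening tool.** Correct. A reader might infer that the arithmetic biases the nomogram, but its inputs in section 1.4.5 are grip strength, sedentary time and BMI. Even for H1 the artefact needs absolute gain not to rise in proportion to baseline. If gain were proportional, the percentage scale would not create it, and the protocol does not settle which holds.

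**The size is assumed.** Also correct. Quoting only 22 to 37% would show the upper part of the range; with little true variation between people the share is 2 to 8%.

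**The statistical analysis plan may settle the model.** It may fix the fitted terms, but the population and the outcome are fixed in H1 itself.

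**Conclusion.** The point holds as a mismatch between design and claim. H1 is confined to trainees, no section gives Sub-study 1 a comparison with the control arm, and the output is to be used as if it identified benefit from training. The model can forecast gain under the programme but cannot separate prognosis from training effect.

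About 2 to 37% of 3% responders would have reached the cut untrained, under the assumed SD, untrained mean and uniform 3-point effect. The 24% at the 1% cut rests only on the stated CV and a normal error. The odds ratio of about 1.4 to 1.6 applies only to H1's baseline-BMD prediction, at the assumed baselines and gains.

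A reader might go further and infer that the main trial result is affected. It is not: the randomised between-arm comparison of BMD does not depend on H1. The change should be made, because it uses data already planned and decides whether the central claim of Sub-study 1 can be supported.

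**What to change.** Fit Sub-study 1 in both randomised arms with arm, predictor and arm-by-predictor terms. Use T2 lumbar spine BMD in g/cm2, adjusted for baseline BMD, as the outcome, and keep percentage response as a descriptive summary. Base any responder claim, and the nomogram, on the predicted difference between arms.

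If the interaction is too imprecise, present the model as prognostic under the programme and remove the responder and response-to-training wording from sections 1.4.2, 1.4.5 and 3.2.1.

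**Cost.** No new data; a different model and edits to those three sections. The price is precision: with equal arms the interaction is a difference of two independent slopes, so its standard error is about √2 = 1.4 times that of the single-arm slope. The prognostic fallback may therefore be where the sub-study ends, and it should be written in now.

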3.2.2 H2 (Sub-study 2)

A nonlinear relationship exists between actual RT dose and outcomes, potentially exhibiting a J- or U-shaped curve. Adherence is operationalised as the proportion of planned sessions completed and mean training-intensity attainment; dose is quantified as cumulative resistance-training volume. We expect that as dose increases from low to moderate, outcomes (e.g., BMD change) improve substantially, but beyond a certain high dose, marginal benefits plateau or decline, indicating an optimal dose range.

3.2.3 H3 (Sub-study 3)

Intervention-induced muscle-strength gains significantly mediate BMD improvement. Specifically, grip-strength increase (Δ HGS) partially explains the BMD gains observed in the intervention group, forming the causal chain: smart RT \rightarrow grip-strength improvement \rightarrow bone-density enhancement. We estimate that Δ HGS accounts for approximately 30–50% of the total effect of the intervention on BMD.

3.2.4 H4 (Sub-study 4)

Technology acceptance moderates intervention effects, mediated through training adherence. Participants with greater smart-device experience and more positive attitudes towards the training platform maintain higher adherence and achieve greater BMD and functional improvements; conversely, participants lacking technological experience or finding device use difficult may discontinue training, thereby attenuating overall intervention effectiveness.

3.2.5 H5 (Sub-study 5)

QoL trajectories during the 8-month intervention are heterogeneous, classifiable into at least two typical patterns (e.g., “improvement” and “stability”). Participants in the improvement trajectory are hypothesised to achieve superior clinical outcomes (greater BMD gain and functional improvement) compared with those in the stable trajectory, suggesting that subjective QoL improvement and objective health gains co-occur.

3.2.6 H6 (Sub-study 6)

Preliminary incremental cost-effectiveness analysis demonstrates that the additional cost per unit BMD gain from the smart RT intervention, relative to usual health education, falls within an acceptable WTP threshold. Specifically, the ICER (per 0.01 g/cm² lumbar spine BMD gain) is expected not to exceed the threshold derived from domestic health-economic evaluation standards, confirming that the intervention achieves an acceptable balance between resource investment and health returns.

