2.4 Cost-Effectiveness and Health Economics Framework

2.4.1 Basic types of health economic evaluation

Health economic evaluation assists decision-makers in determining whether medical interventions warrant investment. Three principal types exist. Cost-effectiveness analysis (CEA) compares the costs and natural health outcomes of different interventions—for example, the cost per 1% BMD improvement or per fracture prevented. Cost–utility analysis (CUA) uses the quality-adjusted life year (QALY) as the effectiveness unit, combining survival time and quality of life; cost per QALY gained (ICER) enables cross-disease comparison. Cost–benefit analysis (CBA) monetises health outcomes, directly comparing the monetary value of averted fractures with intervention costs; however, the monetisation of health value remains controversial and limits practical application.

2.4.2 The concept, calculation, and interpretation of the incremental cost-effectiveness ratio (ICER)

ICER is the core metric for evaluating the economic merit of an intervention. It is calculated as: $ICER = (\text{Cost of intervention group} - \text{Cost of control group}) / (\text{Effect of intervention group} - \text{Effect of control group})$. For example, if smart RT costs CNY 500 per person, control costs CNY 100, and the intervention group gains 0.05 QALY with no change in controls, then $ICER = (500 - 100) / (0.05 - 0) = \text{CNY } 8,000/\text{QALY}$.

ICER must be compared against a willingness-to-pay (WTP) threshold. The internationally accepted benchmark is one to three times per-capita GDP. China’s 2024 per-capita GDP of approximately CNY 95,000 [62] yields a threshold of CNY 285,000/QALY (three times GDP). If ICER falls below this threshold, the intervention is considered cost-effective. Special cases: when the intervention is both less costly and more effective (negative ICER), it is “dominant”; when it is costlier and less effective, it should be rejected. Uncertainty is assessed through bootstrap resampling (1,000 iterations) to generate a cost-effectiveness acceptability curve (CEAC).

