2.4.3 Current status of economic evaluation of osteoporosis interventions

Pharmacological interventions—bisphosphonates, denosumab, and teriparatide—have been shown to be cost-effective in both men and women [63]. Schousboe et al. (2007) demonstrated cost-effective outcomes for BMD testing followed by bisphosphonate treatment in older men [64]. Fracture Liaison Services (FLS) are cost-effective across sexes [63]; Ito (2020) showed cost-effective osteoporosis screening in older men with a fall history [65]. Non-pharmacological interventions including vitamin D and calcium supplementation are cost-effective in older adults [63]; Hiligsmann et al. (2016) confirmed the cost-effectiveness of vitamin D–fortified dairy for fracture prevention in France [66]; and Johansson et al. (2008) demonstrated cost-effectiveness for community safety-promotion programmes in hip-fracture prevention [67]. Notably, no dedicated economic evaluation of RT exists—a gap this study aims to fill.

2.4.4 Challenges and methodological choices for economic evaluation of community exercise interventions

Community exercise economic evaluation faces five challenges, each paired with a targeted solution.

Challenge 1 — Cost fragmentation: Equipment depreciation, venue fees, and training costs are dispersed across multiple items. Solution: micro-costing with item-by-item accounting (e.g., smart terminal cost divided by 10 user-sessions; community worker time costed at hourly wage).

Challenge 2 — Delayed long-term effects: Fracture prevention requires 5–10 years of observation. Solution: Markov modelling extrapolation based on BMD improvement-to-fracture risk reduction, using FRAX® for risk calculation and assuming a conservative 3-year effect duration.

Challenge 3 — Multidimensional benefits: Exercise simultaneously improves function and psychological wellbeing. Solution: primary analysis using EQ-5D–derived QALYs, supplemented by CEA (ICER per 0.01 g/cm² BMD gain).

Challenge 4 — Adherence effects: Actual participation rates influence cost-effectiveness. Solution: attendance-adjusted costing with subgroup ICER analysis (50% vs. 80% attendance groups).

[figure not shown]
Challenge 5 — High uncertainty: Solution: probabilistic sensitivity analysis assigning

distributions to key parameters (cost $\pm 20\%$, effect $\pm 10\%$), with 1,000 Monte Carlo simulations generating CEAC curves.

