The final methodological combination: RCT-based collection of 12-month cost/QALY data → Markov model projection of 10-year benefits → probabilistic sensitivity analysis for robustness verification.

Chapter 3 Research Hypotheses and Overall Conceptual Model

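### H6 judges a cost per 0.01 g/cm² of BMD against a threshold given only per QALY, and the EQ-5D behind the primary QALY analysis is in no outcome list or scheduled visit

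*Protocol*

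**What the plan says.** All references are to the protocol.

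- **Hypothesis.** Section 3.2.6 (H6) concerns the added cost per unit of BMD gained over health education: "the ICER (per 0.01 g/cm² lumbar spine BMD gain) is expected not to exceed the threshold derived from domestic health-economic evaluation standards". No value for the threshold follows.
- **Threshold.** Section 2.4.2 cites a benchmark of one to three times GDP per head. It takes "per-capita GDP of approximately CNY 95,000", which "yields a threshold of CNY 285,000/QALY (three times GDP").
- **Policy rule.** Section 1.4.5 says that "when ICER does not exceed one times per-capita GDP, the intervention enters the basic public health service package", with supplementary commercial insurance above that level. It does not say what the ICER is per.
- **Primary economic analysis.** Section 2.4.4 (Challenge 3) specifies "primary analysis using EQ-5D–derived QALYs, supplemented by CEA (ICER per 0.01 g/cm² BMD gain"). QALYs are primary there and BMD is supplementary. The section's closing summary starts from "RCT-based collection of 12-month cost/QALY data", which then feeds a 10-year Markov projection.
- **A third unit.** Section 1.4.2 describes Sub-study 6 as "calculating the marginal cost per 1% BMD improvement based on actual financial data".
- **Uncertainty.** Section 2.4.2 plans 1,000 bootstrap resamples for an acceptability curve. Section 2.4.4 (Challenge 5) assigns "distributions to key parameters (cost $\pm 20\%$, effect $\pm 10\%$), with 1,000 Monte Carlo simulations generating CEAC curves".
- **What is collected.** The outcome lists (3.3.2, 4.4.1, 4.4.2) name SF-36 PCS and MCS as the quality-of-life measures. The questionnaire rows in the 3.3.4 table are SF-36, FES-I and eHLQ/TAM. SF-36 is ticked at all four visits. There is no EQ-5D row.

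**The concern.** An ICER can be judged only against a willingness to pay in the same effect unit. H6 uses BMD, and the only stated threshold uses QALYs. An analyst who follows the text would have to invent a threshold, invent a conversion from BMD to QALYs, or compare two numbers in different units. The last would almost certainly look favourable.

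The QALY route, which could rescue the comparison, relies on an instrument that the plan does not administer. An analysis plan can settle how utilities are scored. It cannot recover a questionnaire that was never given. At stake are one of six stated hypotheses and a rule that would send the intervention either to the public health package or to commercial insurance.

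**Working it through.** **1. The plan's own figures.** Threshold: 3 × 95,000 = CNY 285,000 per QALY. Worked example in 2.4.2: (500 − 100) / (0.05 − 0) = CNY 8,000 per QALY. Both reproduce, and both are per QALY.

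**2. Effect unit by section.**

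| Place | Effect unit | Threshold |
|---|---|---|
| 1.4.2, Sub-study 6 | 1% BMD | none |
| 1.4.5, policy rule | not named | 1 × GDP per head |
| 2.4.2 | QALY | CNY 285,000 |
| 2.4.4, primary analysis | QALY | none beyond 2.4.2 |
| 2.4.4, supplementary analysis | 0.01 g/cm² | none |
| 3.2.6, H6 | 0.01 g/cm² | domestic standard, no value |

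No row pairs a BMD unit with a stated monetary threshold.

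**3. What the mismatch does (illustration only).** Inputs: incremental cost CNY 400 (the example in 2.4.2, not a projection); 3% lumbar spine gain (the expected increase in 1.4.1, treated here as the between-arm difference); baseline BMD 0.70–0.90 g/cm² (assumed).

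Cost per 0.01 g/cm² = 400 / (0.03 × baseline / 0.01)

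- Baseline 0.70: 400 / 2.1 = CNY 190
- Baseline 0.90: 400 / 2.7 = CNY 148

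A literal comparison with CNY 95,000 gives 95,000 / 190.5 ≈ 499 and 95,000 / 148.1 ≈ 641. H6 would pass by a factor of about 500 to 640 because of the unit.

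**4. What a valid comparison would need.** It needs a QALY value per 0.01 g/cm². The break-even value is the cost per 0.01 g/cm² divided by the threshold:

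- At 1 × GDP: 148.1 / 95,000 = 0.0016 to 190.5 / 95,000 = 0.0020 QALY
- At 3 × GDP: 148.1 / 285,000 = 0.0005 to 190.5 / 285,000 = 0.0007 QALY

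If the true value were anywhere from 0.0005 to 0.02 QALY per 0.01 g/cm² (assumed range), the equivalent threshold per 0.01 g/cm² would be:

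- At 1 × GDP: 95,000 × 0.0005 = CNY 47.5 to 95,000 × 0.02 = CNY 1,900
- At 3 × GDP: 285,000 × 0.0005 = CNY 142.5 to 285,000 × 0.02 = CNY 5,700

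The illustrative CNY 148–190 lies inside both ranges, so H6 could pass or fail on a conversion that the protocol does not give.

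**5. Instrument and horizon.** EQ-5D is named in 2.4.4 and is absent from 3.3.2, 3.3.4, 4.4.1 and 4.4.2. Visits are at 0, 4 and 8 months and at T3, which the 3.3.4 table heads as 14 months and the text below it gives as 20 months. None is at month 12. Linear interpolation from T2 to month 12 would put weight (12 − 8) / (14 − 8) = 0.67 on T3 if T3 is at 14 months, and (12 − 8) / (20 − 8) = 0.33 if it is at 20. A 12-month QALY therefore depends on reconciling the T3 date.

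**The case against.** The strongest defence is that H6 is called preliminary and belongs to one nested sub-study, that nothing here touches randomisation, the trial's primary outcomes or safety, and that utility scoring can sit in an analysis plan. Most of that stands, and it limits the severity. It does not supply a threshold in BMD units, and it does not put EQ-5D into the visit schedule.

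It could also be said that the Markov model turns BMD into fracture risk and so into QALYs. Section 2.4.4 does describe that link, but its summary feeds the model with QALY data collected in the trial, and H6 itself is stated per unit of BMD.

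Several stronger readings are tempting and are not supported:

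- **One versus three times GDP is a contradiction.** Section 2.4.2 gives one to three times as a range, and the rule in 1.4.5 can be read as a payer tier within it. An ICER between CNY 95,000 and 285,000 per QALY would count as cost-effective and go to commercial insurance. The real gap is that H6 does not say which level decides it.
- **QALYs cannot be obtained.** SF-36 is collected at every visit and could support a utility score. The protocol does not plan one.
- **No 12-month visit rules out a 12-month estimate.** T2 and T3 bracket month 12, so interpolation is possible once T3 is fixed.
- **The ±10% effect band is shown to be too narrow for the trial's size.** The phrase n < 100 in 1.4.4 describes Sub-study 2. The ±10% is not defined as a range, standard error or 95% limit, and the effect is not said to be BMD. Sampling uncertainty is also covered by the bootstrap in 2.4.2.
- **The acceptability curve drives the insurance decision.** Section 1.4.5 uses the ICER-to-GDP ratio only.
- **Cost per 1% and cost per 0.01 g/cm² conflict numerically.** They are different scales, and reporting both is not an error in itself.

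**Conclusion.** The point holds on two grounds, both visible in the text. H6 compares a cost per 0.01 g/cm² with a threshold quantified only per QALY, and the policy rule leaves its effect unit unnamed, so H6 has no valid decision rule as written. The primary economic analysis names EQ-5D QALYs over 12 months, while EQ-5D is in no outcome list or scheduled visit and no visit falls at month 12.

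The unit mismatch is a plain reading of the protocol and needs no assumption. The factor of about 500 to 640 and the break-even values of 0.0005 to 0.0020 QALY per 0.01 g/cm² are illustrations. They rest on the worked-example cost, the 3% expectation taken as a between-arm difference, and an assumed baseline BMD of 0.70–0.90 g/cm².

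This should be fixed, but it does not threaten the main trial comparison. Section 4.7.1 gives ethical approval as pending, which makes this the convenient time.

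**What to change.** 1. Restate H6 and the rule in 1.4.5 as cost per QALY, and say which threshold within one to three times GDP per head decides H6.
2. Derive utilities from SF-6D scored on the SF-36 already scheduled at all four visits, keeping item-level responses and naming the value set. Alternatively, add EQ-5D to every visit before baseline assessments begin.
3. Set the within-trial horizon at an actual visit, or state that month 12 is interpolated between T2 and T3. Either way, reconcile the 14- and 20-month dates for T3.
4. Report cost per BMD gain descriptively, in one unit, with no pass or fail attached.
5. In the Markov sensitivity analysis, draw the effect from the bootstrap distribution already planned in 2.4.2 in place of a fixed ±10%.

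The cost is protocol wording and SF-6D scoring work, or one more questionnaire per visit if EQ-5D is added. The uncertainty shown may be wider than under the fixed band.
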